Mothers were recruited in maternity wards of the 12 participating hospitals shortly after giving birth and, after consenting, were administered a 30-minute baseline interview. They then were asked to consent to the cash gifts. The "high-cash gift" treatment group mothers (40% of all mothers) are receiving unconditioned cash payments of \$333 per month (\$4,000 per year) via debit card for 52 months. Mothers in the "low-cash gift" comparator group (60% of all mothers) are receiving a nominal payment – \$20 per month, delivered in the same way and also for 52 months. The 40/60 randomization assignment is stratified by site, but not by hospitals, within each of the four sites.

BFY was originally formulated to study the effects of monthly unconditional cash transfers on child development for the first three years of life, with the cash gifts set to be distributed for 40 months (3 years, 4 months). In response to the COVID-19 pandemic and the need to postpone in-person research activities, the cash transfers were extended for an additional year, through 52 months (4 years, 4 months), enabling us to postpone in-person direct child assessments to age 4. Interviews conducted at child ages 1, 2 and 3 are providing information about family functioning as well as several maternal reports of developmentally-appropriate measures of children's cognitive and behavioral development. The current analysis plan includes lab-based assessments at child age 4.

Conditional on participants' consent and our success in securing agreements with state and county agencies, we are also collecting state and local administrative data regarding parental employment, utilization of public benefits such as Medicaid and Supplemental Nutrition Assistance Programs (SNAP), and any involvement in child protective services. (We have worked with state and local officials to ensure to the extent feasible that our cash gifts are not considered countable income for the purposes of determining benefit levels from social assistance programs.)

The compensation difference between families in the high and low cash gift groups will boost family incomes by \$3,760 per year, an amount shown in the economics and developmental psychology literatures to be associated with socially significant and policy relevant improvements in children's school achievement. After accounting for likely attrition, our total

Analysis Plan for Phase 1

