Our basic empirical approach will use the survey and neuroscience data to compare the pooled cross-city \$333/month and \$20/month groups on a wide range of family process and child outcome measures. Because of random assignment, the low cash gift group average outcomes enable us to identify the average outcomes corresponding to the counterfactual state that would have occurred for individuals in the high cash gift group if they had not been offered the additional \$313/month income supplement. Therefore, differences in outcomes for the high compared with the low group (after random assignment) can be interpreted as estimates of causal treatment effects of the \$313/month higher income (regardless of whether treatment-group participants actually expend all of the funds.) These are commonly known as intent-to-treat effects.

Estimation strategy. We illustrate our approach to estimation in a simple regression framework. The “Intent-To-Treat effect” (ITT) is captured by the estimate of the coefficient π_1 in a regression of some child or family process outcome (Y) on a dichotomous indicator for assignment (Z) to the high payment group as in (1).

$$(1) Y = Z\pi_1 + X\beta_1 + \varepsilon_1$$

We have experienced extremely low rates of “non-compliance” with the offer of cash gifts paid via the debit cards, with less than 10 of the 1,000 participants never having charged anything on their debit cards. We will adjust standard errors using robust variance estimation techniques (Cameron et al. 2008). We will estimate (1) without and then with baseline demographic child and family characteristics (X) to improve the precision of our estimates by accounting for residual variation.

Baseline measures, all gathered prior to random assignment, have been checked for adequate variation and sufficient independence from other baseline measures. They include: dummy variables for three of the four sites; mother’s age, completed schooling, household income, net worth, general health, mental health, race and Hispanic ethnicity, marital status, number of adults in the mother’s household, number of other children born to the mother, whether the mother smoked or drank alcohol during pregnancy and whether the father is currently living with the mother; and child’s sex, birth weight, gestational age at birth, and birth order.

Analysis Plan for Phase 1

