We will apply our regression estimation strategy to the assessment-based measures of cognitive, language, self-regulation, and socio-emotional functioning and EEG measures of brain activity as outlined in Appendix Tables 7. Further information on the EEG hypotheses and analysis plan is described in the section titled *Age-4 Resting EEG Hypotheses and Analysis Plan* below. To investigate family process impacts, we will apply our estimation strategy to maternal and family measures gathered at child ages 1, 2, 3, and 4 as shown in Appendix Table 8.

Attrition. The greatest threat to internal validity is potential bias from sample attrition overall, within site, and differential attrition rates by treatment status overall and within site. We will carefully track response rates by site, by treatment status across sites, and then treatment status within site. Response rates have been very high at ages 1. Of the original 1,000 recruited participants, we secured interviews with 931 at age 1, 922 at age 2, and 922 again at age 3. We expect at least 800 completed cases in our age-4 lab visit.

We will also conduct sensitivity checks to evaluate whether missing data might be biasing estimates. Most sample attrition that is systematically related to our outcomes of interest (Y) would presumably also be related to the distribution of baseline characteristics (X), and so bias due to sample attrition would be evident if our estimates are sensitive to conditioning on baseline characteristics. Some attrition may be due to time-varying (or unobserved) characteristics, and we can approach this problem in two ways. First, we will examine the sensitivity of our results to worst-case bounds, which enable us to bracket the true effects of our treatment without imposing any assumptions about the unobserved outcomes of participants (Manski, 1989; Manski, 1990; Manski, 1995). A second approach to addressing the problem of missing data will be to use multiple imputation strategies with all available data, (including all survey and administrative data on outcomes and predictor variables). Multiple imputation is an appropriate method if, conditional on all observed information, data are missing at random. Finally, because we have permission to collect administrative data from over 75% of mothers, we will be able to compare survey respondents and survey non-respondents on formal earnings and receipt of income from social programs.

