Statistical power. The compensation difference between families in the high- and low-cash gift groups amounts to \$313 per month and \$16,276 over the course of the 52 months. This amount is in the range of income increases associated with child impacts of around .20 sd in studies of welfare experiments and the EITC ([name], Morris & Rodrigues, 2011; Morris, [name], Clark-Kauffman, 2005; Dahl & Lochner, 2012). After accounting for likely 20% attrition in the age-4 lab visit, and in the absence of adjustments for sample clustering within hospitals or increased precision owing to the inclusion of baseline covariates in our impact estimates, the sample size of 800 at age 4, divided 40%/60% between high and low payment groups, provides 80% statistical power to detect a .219 sd impact at $p < .05$ in a two-tailed test on cognitive functioning and family processes. The use of baseline covariates in estimation models will improve this power, while the use of bootstrap standard errors will decrease it. Based on exploratory analyses of age-3 cognitive outcomes in the Fragile Families study, we expect that these two offsetting factors will have little net impact on the size of our estimated standard errors.

Multiple comparisons. One strength of our study is the collection of survey, neuroscience lab and administrative data on a wide range of outcomes and explanatory pathways. However, the probability of rejecting a true null hypothesis for at least one outcome is greater than the significance level used for each test. We will address the possibility of false positives while minimizing the reduction in statistical power to detect meaningful effects. Best-practice methods differ across disciplines so we will draw from multiple approaches with the goal of ensuring that results from one approach are consistent with results from others (Romano & Wolfe, 2005; Porter, 2018; Benjamini, 2010; Holm, 1979, Westfall & Young, 1993; Schochet, 2008). Where possible we have aggregated measures used to test our pre-registered hypotheses into indexes. In the case of related measures that cannot be aggregated into a single index, we will estimate the statistical significance of the entire family (“familywise error rate”) using stepdown resampling methods in Westfall and Young (1993; Westfall, Tobias, Wolfinger, 2011). Pre-registered clusters of measures are identified with grey bars in appendix tables.

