"Take-up" of the cash gifts is virtually universal, with fewer than six families never having used their debit cards by child age 3. We will adjust standard errors using robust variance estimation techniques (Cameron et al. 2008). We will estimate (1) without and then with baseline demographic child and family characteristics (X) to improve the precision of our estimates by accounting for residual variation. These baseline measures, all gathered prior to random assignment, have been checked for adequate variation and sufficient independence from other baseline measures. They include: dummy variables for three of the four sites; mother's age, completed schooling, household income, net worth, general health, mental health, race and Hispanic ethnicity, marital status, number of adults in the mother's household, number of other children born to the mother, whether the mother smoked or drank alcohol during pregnancy and whether the father is currently living with the mother; and child's sex, birth weight, gestational age at birth, birth order and interview/assessor ID. For child outcomes we also control for child's age in months at the time of the survey/assessment.

Analysis Plan for Phase 2

We will apply our regression estimation strategy to the assessment-based measures of cognitive, language, self-regulation, and socio-emotional functioning and EEG measures of brain activity gathered at ages 6 and 8. To investigate family process impacts, we will apply our estimation strategy to maternal and family measures gathered at child ages 6 and 8.

Attrition. The greatest threat to internal validity is bias from sample attrition overall, within site, and differential attrition rates by treatment status overall and within site. We will carefully track response rates by site, by treatment status across sites, and then treatment status within site. Response rates were very high for the ages 1-3 data collections and varied across measures at age 4. Of the original 1,000 recruited participants, we secured interviews with 931 at age 1, 922 at age 2, and 922 again at age 3. By age 4, 5 mothers and 5 children had died and we gathered information on between $n=634$ (for child EEG) to $n=882$ (for maternal reports of behavior problems) of the remaining 990 families.

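### In the Phase 1 SAP, movement between unadjusted and adjusted estimates is read as the sign of attrition bias, but chance imbalance also moves them and drop-out unrelated to measured covariates does not

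*SAP*

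**What the plan says.** The Phase 1 SAP (Estimation strategy) fits the intent-to-treat regression first without and then with baseline characteristics. The stated reason for including them is precision: "to improve the precision of our estimates by accounting for residual variation". The Attrition section then gives the same pair of estimates a second use. It argues that most outcome-related attrition would presumably also be related to the baseline characteristics, and concludes that "bias due to sample attrition would be evident if our estimates are sensitive to conditioning on baseline characteristics". It does not say how much movement counts as sensitive, and gives no standard error or test for the movement.

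The section does more than this. It tracks response rates by site and arm. It accepts that some attrition may come from unobserved or time-varying causes, and for that it plans worst-case bounds and multiple imputation. It also compares respondents with non-respondents on administrative records.

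On design, the Project Summary says: "The 40/60 randomization assignment is stratified by site, but not by hospitals, within each of the four sites". The sentence at issue is current text. The July 2025 addendum changes the control variables and leaves it in place. The Phase 2 Attrition section does not contain it.

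**The concern.** The gap between the unadjusted and adjusted estimates among completers is, in essence, the arm difference in the covariate-predicted part of the outcome. That difference has two sources: imbalance present by chance when mothers were randomised, and imbalance created later by drop-out. Only the second has to do with attrition. Because assignment was stratified by site alone, every other prognostic covariate can be imbalanced by chance. Because the covariates are included for precision, they are expected to predict the outcome, so chance imbalance will move the estimate.

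The other direction is also weak. If drop-out depends on something the covariates do not capture, the estimate can be biased and still not move.

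The SAP ranks attrition as the leading danger to internal validity. A reader given this rule could be falsely reassured by stable estimates or falsely alarmed by unstable ones.

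**Working it through.** **Inputs from the SAP (Phase 1, Statistical power).** "the sample size of 800 at age 4, divided 40%/60% between high and low payment groups", that is 320 and 480; "After accounting for likely 20% attrition in the age-4 lab visit"; "provides 80% statistical power to detect a .219 sd impact at $p < .05$ in a two-tailed test".

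**Inputs assumed.** The documents give neither the covariate R-squared nor any difference in attrition between arms. R-squared is taken as .1, .2 and .3. Drop-out patterns are stated case by case.

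**1. The plan's own figure.** SE = sqrt(1/320 + 1/480) = .0722 SD. The minimum detectable effect is (1.960 + 0.842) × .0722 = .202 SD. The Phase 1 figure of .219 does not reproduce; the Phase 2 figure of .20 for the same size and split does. This is a separate matter. The SE implied by .219 is .219/2.802 = .078, which would make the chance movement below about 8% larger.

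**2. Movement with no attrition bias.** Var(unadjusted − adjusted) = R² × SE², so its SD is sqrt(R²) × .0722.

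| R² | SD of movement | 95% range |
|---|---|---|
| .1 | .023 | ±.045 |
| .2 | .032 | ±.063 |
| .3 | .040 | ±.077 |

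Simulation (1,000 randomised 40/60, 20 covariates, 20% drop-out) gave .026, .034 and .040. At the 634 children with age-4 EEG data reported in the Phase 2 Attrition section, the formula gives .026 to .044.

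**3. Drop-out driven by the outcome, in opposite directions by arm, true bias .10 SD.** Only the share R² shows as movement: .010, .020, .030. Divided by the chance SD this is 0.44, 0.62, 0.76. A test calibrated at 5% would detect the bias 7%, 10% and 12% of the time. Simulation of the same case gave up to 13%.

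**4. Drop-out through the covariates, same direction in both arms.** Mean movement = (difference in attrition rate) × (gap between drop-outs and stayers in index SDs) × sqrt(R²). R² cancels when this is divided by the chance SD.

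| Attrition difference | Gap | Movement / chance SD | Detection at 5% |
|---|---|---|---|
| 5 points | 0.5 SD | .025/.0722 = 0.35 | 6% |
| 10 points | 0.5 SD | .05/.0722 = 0.69 | 11% |
| 10 points | 1 SD | .10/.0722 = 1.39 | 28% |

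**5. Drop-out on an unobserved factor only.** In simulation the true bias was .086 to .097 SD and the mean movement about zero. Movement exceeded .02 SD (an illustrative cut-off; the SAP has none) in 42%, 57% and 63% of trials, against 45%, 54% and 59% with no bias.

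**6. Strong opposite-direction drop-out through the covariates.** If the whole .10 SD bias runs through the covariates, the ratio is .10/(sqrt(R²) × .0722) = 4.4, 3.1, 2.5, and detection is 99%, 87% and 72%. Simulations of such drop-out gave 67% to 100%, with about zero bias left in the adjusted estimate.

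**7. Completers minus all randomised.** The arm difference in the index among completers, minus the same difference among all 1,000, has chance SD sqrt(R²) × sqrt(1/192 − 1/240) = .0323 × sqrt(R²), where 192 = .24 × 800 and 240 = .24 × 1,000. That is .010, .014 and .018, less than half the values in step 2. Detection in step 3 becomes 17%, 28% and 40%. In the last row of step 4 the ratio is .10/.0323 = 3.10 and detection is 87%.

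**The case against.** The strongest reply is that the sentence rests on a premise, that most outcome-related attrition is also related to baseline characteristics, and should be judged under it. Step 6 shows that when the premise holds and selection is strong and opposite by arm, the estimate does move and a formal test would usually find it. That stands. It rules out the broader reading a reader might take, that the check can never tell bias from no bias or that chance always dominates. Whether chance dominates depends on R-squared and on the drop-out pattern, and the documents give neither. Even under the premise, though, modest same-direction drop-out is mostly missed (step 4), and the SAP plans no test of the movement.

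A second reply is that other checks are planned and none depends on this one. That also stands: attrition is not left unexamined. The SAP concedes unobserved causes and does not say that stable estimates prove the absence of bias. The other checks do not rescue this inference, however. Multiple imputation assumes data missing at random, and the administrative comparison covers earnings and social-programme income, not child outcomes.

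A third reply is that the arms will be compared on all baseline characteristics within site. That bears on imbalance at randomisation, but the SAP does not subtract it from the imbalance among completers, so the two sources of movement stay mixed.

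Finally, the replacement is itself weak in step 3, missing the bias more often than not. This is true and has to be stated with it.

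**Conclusion.** The concern holds in a limited form. Movement between the unadjusted and adjusted age-4 estimates is not by itself evidence of attrition bias, and lack of movement is not evidence against it. At 800 children, chance alone moves the estimate with an SD of about .023 to .040 SD. The check therefore discriminates poorly when selection is modest or runs mainly outside the measured covariates: about 7% to 13% detection of a .10 SD outcome-driven bias, even if the movement were formally tested. It does work for strong opposite-direction selection through the covariates, where adjustment removes the bias anyway.

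A reader might infer that the age-4 effect estimates are themselves compromised. The documents do not support that. The fault is in the interpretation of one attrition check in Phase 1; equation (1) is unaffected. The figures rest on assumed R-squared of .1 to .3, the stated 20% attrition, and the drop-out patterns set out above.

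**What to change.** Replace the sentence in the Phase 1 Attrition section with the following analysis.

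- Fit the covariate part of equation (1) and compute the resulting prognostic index for all randomised mothers. Use only pre-randomisation covariates, leaving out the assessor and age-at-assessment controls added in July 2025. State how missing baseline items are handled.
- Report the arm difference in the index among completers minus the arm difference among all randomised, with a bootstrap standard error.
- State that a small value rules out only attrition related to measured baseline variables, and that movement between unadjusted and adjusted estimates is not by itself evidence of attrition bias.

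The cost is a little extra analysis on baseline data already collected, and a dated addendum of the kind the SAP already uses. The check remains blind to unmeasured causes of drop-out, so the bounds and imputation analyses stay as planned.

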More consistent quasi-experimental evidence of income effects comes from the welfare-to-work experiments of the 1990s, most of which increased employment and some of which also increased family income with earnings supplements. Although there were no comparable positive effects on achievement or high school completion among older children, in the case of low-income children making the transition into school, these studies indicated that income increases improved achievement and schooling outcomes, with a \$4,000 increase in annual income (in current dollars) for 2-3 years increasing school achievement by .18 standard deviation units.^{19,20} Our proposed experiment is powered to detect effects of this magnitude.

Recent quasi-experiments have taken advantage of other sources of plausibly exogenous changes in family income, suggestive of what an unconditional cash transfer might provide. Studies exploiting variations in the timing of state- and province-specific expansions of U.S. and Canadian tax benefits for low-income families show that receipt of these types of cash gift payments contribute to higher test scores among elementary school children.^{21,22} In other work, casino disbursements to Native American families have been linked to increased educational attainment for adolescents.²³ Although the magnitude of income increases in these studies was only several thousand dollars, the increases account for a substantial share of a poor family's income—often 20% or higher—and the effects on children's outcomes were large enough to be meaningful.

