Statistical power. The compensation difference between families in the high- and low-cash gift groups amounts to \$313 per month and \$23,788 over the course of the 76 months. The annual equivalent of this amount is in the range of income increases associated with child impacts of around .20 sd in studies of welfare experiments and the EITC ([name], Morris & Rodrigues, 2011; Morris, [name], Clark-Kauffman, 2005; Dahl & Lochner, 2012). After accounting for likely 20% attrition in the age-6 lab visit, and in the absence of adjustments for sample clustering within hospitals or increased precision owing to the inclusion of baseline covariates in our impact estimates, a sample size of 800 at age 6 or 8, divided 40%/60% between high and low payment groups, provides 80% statistical power to detect a .18 sd impact on cognitive functioning and family processes at $p < .05$ in a one-tailed test and a .20 sd impact at $p < .05$ in a two-tailed test. For our planned EEG measurements (see below), we anticipate a sample size that is closer to 700 than 800. A sample size of 700 at age 6 or 8, divided 40%/60% between high and low payment groups, provides 80% statistical power to detect a .19 sd impact on cognitive functioning and family processes at $p < .05$ in a one-tailed test and a .22 sd impact at $p < .05$ in a two-tailed test.

Multiple comparisons. One strength of this study is the collection of survey, child assessment, neuroscience and administrative data on a wide range of outcomes and explanatory pathways. However, the probability of rejecting a true null hypothesis for at least one outcome is greater than the significance level used for each test. We will address the possibility of false positives while minimizing the reduction in statistical power to detect meaningful effects. Best-practice methods differ across disciplines so we will draw from multiple approaches with the goal of ensuring that results from one approach are consistent with results from others (Romano & Wolfe, 2005; Porter, 2018; Benjamini, 2010; Holm, 1979; Westfall & Young, 1993; Schochet, 2008). Where possible we have aggregated measures used to test our pre-registered hypotheses into indexes. In the case of related measures that cannot be aggregated into a single index, we

Analysis Plan for Phase 2

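### Phase 1's .219 SD detectable effect should read .20 SD on its own inputs, and Phase 2 does not explain its forecast of about 700 EEG children beside the 634 obtained at age 4

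*SAP*

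**What the plan says.** **SAP, Analysis Plan for Phase 1, Statistical power.** The starting point is the expected loss of a fifth of the 1,000 families: "After accounting for likely 20% attrition in the age-4 lab visit". The calculation then uses "the sample size of 800 at age 4, divided 40%/60% between high and low payment groups", which "provides 80% statistical power to detect a .219 sd impact" at .05 "in a two-tailed test on cognitive functioning and family processes". The paragraph says that the figure includes neither a clustering adjustment nor a gain from baseline covariates. It adds that these two influences should roughly cancel. It also says that the cash difference is in the range linked to child impacts of around .20 SD in the studies it cites.

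**SAP, Analysis Plan for Phase 2, Statistical power.** With the same n, split, alpha, power and exclusions, 800 children "provides 80% statistical power to detect a .18 sd impact on cognitive functioning and family processes" one-tailed, and .20 SD two-tailed. For EEG at ages 6 and 8, "we anticipate a sample size that is closer to 700 than 800", and at 700 the plan gives .19 SD one-tailed and .22 SD two-tailed.

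**SAP, Analysis Plan for Phase 2, Attrition.** By age 4, information had been gathered on 634 of the remaining 990 families for child EEG, and on 882 for maternal reports of behavior problems.

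**The concern.** The two plans sit in one SAP and give different two-tailed detectable effects, .219 and .20 SD, for what is stated to be the same case. At most one can be right.

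Readers will use the figure to judge null results at age 4. With .219 SD, a design benchmarked against effects of around .20 SD seems to fall short, and a null is easier to put down to low power. With .20 SD, that explanation is weaker.

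The EEG question is different in kind. The mid-to-high-frequency power composite is a primary outcome at ages 6 and 8. Its stated sensitivity rests on a sample 66 children larger than the age-4 yield reported in the same plan (700 - 634 = 66), and the plan does not say where the extra children would come from.

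**Working it through.** **Formula.** For two group means, with the effect in SD units (SD = 1) and a 40/60 split:

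MDE = (z_alpha + z_power) / sqrt(0.4 × 0.6 × n) = (z_alpha + z_power) / sqrt(0.24 n)

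Inputs from the two Statistical power sections: 80% power (z = 0.842), and alpha .05 two-tailed (z = 1.960, sum 2.802) or one-tailed (z = 1.645, sum 2.486).

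**Step 1. Phase 1, n=800, two-tailed.**

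- 0.24 × 800 = 192, and sqrt(192) = 13.856.
- MDE = 2.802 / 13.856 = **.202 SD**, against the stated .219. The noncentral t gives .2024.
- Power at .219 SD: .219 × 13.856 = 3.035, and 3.035 - 1.960 = 1.075, which gives **85.9%**, not 80%.
- n for which .219 SD is the two-tailed MDE: (2.802 / .219)² / 0.24 = **about 682**.

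**Step 2. Can another reading of the inputs give .219 at n=800?**

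| Variant | MDE (SD) |
|---|---|
| One-tailed | .179 |
| 50/50 split | .198 |
| One-third / two-thirds split | .210 |
| 30/70 split | .216 |
| 85% power | .216 |
| 90% power | .234 |
| Alpha .025 two-tailed | .222 |
| 20% attrition taken off twice (n=640) | .226 |

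None gives .219. It would take an alpha of about .028, or a design effect of (.219 / .2022)² = 1.17. The paragraph sets alpha at .05 and says that clustering is not included.

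**Step 3. Do the Phase 2 figures reproduce?**

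| n | Test | Stated (SD) | Computed MDE (SD) | Power at stated value |
|---|---|---|---|---|
| 800 | one-tailed | .18 | .179 | 80.2% |
| 800 | two-tailed | .20 | .202 | 79.1% |
| 700 | one-tailed | .19 | .192 | 79.3% |
| 700 | two-tailed | .22 | .216 | 81.4% |

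All four agree with their own inputs. Only .219 does not.

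**Step 4. EEG at the age-4 yield, n=634.**

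- 0.24 × 634 = 152.16, and sqrt(152.16) = 12.335.
- One-tailed MDE = 2.486 / 12.335 = **.202 SD** (stated .19 at n=700).
- Two-tailed MDE = 2.802 / 12.335 = **.227 SD** (stated .22 at n=700).
- Power for .19 SD one-tailed: .19 × 12.335 - 1.645 = 0.699, which gives **about 76%**.
- Power for .22 SD two-tailed: .22 × 12.335 - 1.960 = 0.754, which gives **about 77%**.

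**The case against.** On .219, the best defence is that little depends on it. The error runs in the cautious direction, the sample size is fixed, age-4 counts have already been reported, and the later plan in the same SAP prints .20. All of that stands, and it limits the consequence. It does not make the figure right, and the SAP still gives two answers to one question.

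On EEG, the defence is that about 700 is a forecast for different ages, that the yield at 6 and 8 may differ from that at 4, and that 634 is openly reported a few paragraphs before. This also stands. The point is therefore a missing justification, not a wrong calculation.

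A reader might infer four stronger things that the documents do not support:

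- **That the stated detectable effects are wrong in general.** The four Phase 2 figures reproduce.
- **That EEG power at ages 6 and 8 is overstated as a fact, and more so because the primary uses eyes-closed data.** The yield at those ages is not known from the documents, and no eyes-closed yield is given.
- **That .18 SD is wrong for the executive-function measures because three scores share one multiplicity cluster.** The appendix table of child hypotheses plans a confirmatory factor analysis and a test of the common factor at both ages. The Phase 2 text reserves step-down testing for measures that cannot be combined. The table header also puts same-wave measures under adjustment, so the role of the single scores could be clearer. A Bonferroni figure would in any case be only an upper bound for the planned resampling method.
- **That the Protocol's claim about .18 SD fails.** The Significance section says "Our proposed experiment is powered to detect effects of this magnitude" but gives no n, alpha or sidedness there. Judging it at n=800 two-tailed brings in assumptions from later plans for other ages.

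**Conclusion.** The Phase 1 figure is wrong as written. On its stated inputs the detectable effect is .202 SD, an overstatement of about .017 SD (.219 - .202), and power at .219 SD is about 86%. The design is slightly better than the plan says and essentially meets the benchmark of around .20 SD. The result needs only the stated n, split, alpha and power, with no clustering or covariate adjustment.

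The EEG point is real but smaller. If the yield at ages 6 and 8 matched age 4, the detectable effects would be about .01 SD larger than stated: .202 - .192 = .010 one-tailed and .227 - .216 = .011 two-tailed. Power at the stated values would be about 76% and 77%. The one-tailed effect would then sit at the .20 SD benchmark instead of just under it. This rests on taking 634 as the analysable number. The plan does not say whether 634 is counted before or after artifact rejection.

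**What to change.** 1. In the Phase 1 Statistical power section, replace .219 with .20 SD (two-tailed, n=800), with a dated note that this corrects a calculation and agrees with Phase 2. If .219 came from an assumption that the paragraph does not state, give that assumption instead.
2. In the Phase 2 Statistical power section, either say why about 700 EEG cases are expected after 634 at age 4, or keep the n=700 figures and add a second line for n=634: .20 SD one-tailed and .23 SD two-tailed, with power of about 76% for .19 SD one-tailed and 77% for .22 SD two-tailed.

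Both are text edits. The design, data collection, tests and hypotheses stay as they are. The only cost is that the added EEG line is slightly less favourable than the figures now printed.

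### The Phase 1 power figure does not follow from its inputs: 800 children split 40/60 give 80% two-tailed power for .202 sd, not .219, and Phase 2 prints .20 for the same calculation

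*SAP*

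**What the plan says.** In the Phase 1 plan, under Statistical power, the SAP sets out its inputs in a single sentence. The sample is already net of dropout ("After accounting for likely 20% attrition in the age-4 lab visit"), and the design is "the sample size of 800 at age 4, divided 40%/60% between high and low payment groups". The calculation is made "in the absence of adjustments for sample clustering within hospitals or increased precision owing to the inclusion of baseline covariates in our impact estimates". The test is two-tailed at .05. On that basis the design "provides 80% statistical power to detect a .219 sd impact at" that level. Just before this, the same paragraph says the cash difference is in the range linked to "child impacts of around .20 sd in studies of welfare experiments and the EITC".

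The Phase 2 plan has a matching Statistical power paragraph. It takes "a sample size of 800 at age 6 or 8, divided 40%/60% between high and low payment groups", with the same 80% power and the same exclusion of clustering and covariate gain. It reports .18 sd "in a one-tailed test and a .20 sd impact at" the .05 level two-tailed. It adds figures for 700 children: .19 one-tailed and .22 two-tailed.

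**The concern.** The two paragraphs describe the same calculation and print different results, .219 and .20. Read together, they also imply that 800 children detect .219 sd and 700 detect .22 sd under the same two-tailed test, as if 100 more children made almost no difference. At least one figure must be wrong or must rest on an assumption that is not stated.

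What is at stake is how the age-4 wave's sensitivity is understood. The Phase 1 figure stands next to the benchmark of about .20 sd. If .219 is taken at face value, the wave falls somewhat short of that benchmark. On the stated inputs it roughly meets it. The SAP also commits to releasing the data to outside researchers, who may take the planning figures as they stand.

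**Working it through.** **Inputs**, all from the Phase 1 Statistical power paragraph:

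- N = 800 split 40/60, so 320 high-cash and 480 low-cash.
- Effects in sd units, so SD = 1.
- Two-tailed alpha .05 (z = 1.960) and 80% power (z = .842).
- No design effect and no covariate gain.

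**Formula.** Detectable effect = (z for alpha + z for power) × sqrt(1/n1 + 1/n2).

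**Attempt to reproduce the Phase 1 figure**

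- Standard error = sqrt(1/320 + 1/480) = .07217.
- Detectable effect = (1.960 + .842) × .07217 = **.202 sd**. The noncentral t gives .2024.
- The stated .219 is not reproduced: .219/.202 = 1.08, about 8% too large.

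**What .219 would correspond to**

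- Power at .219 with 800 children: Φ(.219/.07217 − 1.960) = 85.9%.
- Children needed for 80% power at .219: (2.802/.219)² / (.4 × .6) = about 682, some 15% fewer than 800.
- Design effect needed to turn .202 into .219: (.219/.2022)² = 1.17.

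**Other readings tried at N = 800** (two-tailed .05, 80% power, 40/60 split unless noted)

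| Variant | Detectable effect (sd) |
|---|---|
| One-tailed | .179 |
| 50/50 split | .198 |
| 1:2 split | .210 |
| 30/70 split | .216 |
| 85% power | .216 |
| 90% power | .234 |
| Two-tailed alpha .025 | .222 |

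None gives .219.

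**Phase 2 figures by the same formula**

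| N | Test | Stated | Recomputed |
|---|---|---|---|
| 800 | two-tailed | .20 | .202 |
| 800 | one-tailed | .18 | .179 |
| 700 | two-tailed | .22 | .216 |
| 700 | one-tailed | .19 | .192 |

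All four agree after rounding. Phase 2 therefore matches the simple formula, and Phase 1 is the outlier.

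**Power at the .20 benchmark**

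- On the stated inputs: Φ(.20/.07217 − 1.960) = 79.1%.
- If .219 were the true 80% point: Φ(2.802 × .20/.219 − 1.960) = 72.5%.

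**The case against.** The arithmetic is not in dispute. The case on the other side concerns how much the error matters and how it should be corrected.

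- **The error is conservative and has no analytic effect.** It overstates the detectable effect and understates power. Recruitment had already closed at 1,000, and the 800 comes from expected attrition, not from .219. No model, endpoint or alpha changes. This stands.
- **Nothing in the SAP makes the planned figure a threshold for reading null results, and the sample actually obtained differs by measure.** The Phase 2 Attrition paragraph reports age-4 data on 634 families for EEG up to 882 for maternal reports of behavior problems. The same formula gives .227 and .193 sd for these. For EEG, .202 is further from the achieved value than .219 is. This also stands: .202 is the right answer to the stated calculation, not a yardstick for every age-4 outcome.
- **The benchmark is approximate.** The SAP does not itself compare .219 with it, and the gap between 72.5% and 79% power is modest. The Protocol's Significance section also claims power for .18 sd. At N = 800, two-tailed, power there is Φ(.18/.07217 − 1.960) = about 70%, so correcting .219 does not make that claim good. This is fair, and it limits how much weight the benchmark comparison can carry.
- **The origin of .219 is unknown.** A sample near 682 or a design effect near 1.17 would fit. Neither is stated, and the sentence expressly excludes a clustering adjustment. The remarks on covariates and bootstrap standard errors come after the figure and expect the two to roughly offset. This affects the form of the fix, not the finding.

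**Conclusion.** The concern holds. With 320 and 480 children, SD 1, two-tailed .05, 80% power and no adjustments, the detectable effect is .202 sd. The Phase 1 figure of .219 is wrong as written, by .017 sd or about 8%, and Phase 2 contradicts it with the correct rounded value for the same design. No input had to be assumed, because each is stated in the Phase 1 paragraph itself. The Phase 1 plan is reissued in the July 2025 document with its own addendum and is not marked as superseded, so this is current text. The consequence is for consistency and interpretation. The trial is not made underpowered, and no planned analysis is affected.

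**What to change.** Correct the Phase 1 figure to .202 sd (or .20, to match the rounding in Phase 2). If .219 was meant to carry a smaller sample or a design effect, state that assumption and its value, and delete the words saying that no such adjustment was made. The SAP records later changes to the preregistered plans in dated addenda, so a short dated correction note is a better vehicle than overwriting the 2022 text. It would help if the note also pointed to the achieved age-4 sample for each measure, since detectable effects at 634 and 882 families differ from the planned value. The cost is one number and a sentence of explanation, with no change to data collection or analysis.
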